**Table 4: Schedule of Visits and Procedures** 

# **SCHEDULE OF EVENTS**

PROCEDURES	Screening (Day -35 — Day -1)	Visit 1 Baseline (Day 0)	Visit 2  Week 2 ±3 days (Day 14)	Visit 3 Week 4 ±5 days (Day 28)	Visit 4 Week 8 ±5 days (Day 56)	Visit 5 Week 12/ET  ±5 days (Day 84)
Informed Consent	X					
Demographics/Smoking						
Medical History	X	X				
Medication History	X	X				
Inclusion/Exclusion	X	X				
Brief Physical Examination	X	$X^3$				X
Chemistry, Hematology, PT/PTT	X	$X^3$				X
Urine Pregnancy Test	X	$X^3$		X	X	X
Methemoglobin 	X	X	X			X
Blood Pressure and Pulse	X	X	X	X	X	X
Wart Counts	X	X	X	X	X	X
Tolerability Evaluation 		X	X	X	X	X
Instruct on Study Drug Application and Provide Subject Instructions		X				
Dispense Dosing Diary		X		X	X	
Collect Completed Dosing Diary				X	X	X
Study Drug Dispensed		X		X	X	
Study Drug Collected				X	X	X
Subject Compliance			X	X	X	X
Concomitant Medications		X	X	X	X	X
Adverse Events	X	X	X	X	X	X

All visit dates are in reference to Baseline, e.g., Visit 2 occurs two weeks (14 days) after Baseline visit.

<sup>2 All Week 12 procedures should be completed for subjects who prematurely discontinue.

<sup>3 If the Baseline Visit is within 7 calendar days of the Screening visit, Physical Examination, Chemistry, Hematology, PT/PTT, and UPT do not need to be repeated.

<sup>4 Collected via pulse co-oximetry at site.

<sup>5 Tolerability Assessments are defined in Section 4.3

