## 4.4. Assessment Windows

## 4.4.1. Study Day

When study day is used for display or in comparisons the following algorithm will be used:

- study day = date of assessment date of first dose of study medication +1, if date of assessment ≥ first dose date.
- study day = date of assessment date of first dose of study medication, if date of assessment < first dose date.

Note that this definition differs from the protocol in that the date of first dose of study medication is Day 1. The day before the date of first dose of study medication is Day -1. Study day for analysis is defined as per SDTM definition which does not include a study day Day 0.

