## 8.2.8. Time to Complete Clearance of Baseline Warts

The time to complete clearance of baseline warts is calculated as the number of days between the date of first dose of study medication and the date that the baseline wart count is 0. Subjects who do not have clearing of baseline warts will be censored at the date of their last study assessment.

Kaplan-Meier (KM) estimates of clearance rates at Week 2, Week 4, Week 8 and Week 12 and their 95% CIs will be presented by treatment group. Vehicle Gel subjects will be separated into QD and BID groups. For estimates by week, week will be defined by the maximum day allowable by the visit windows (e.g., the summary for Week 2 will count all subjects with clearance on or before Day 18.) Because clearance is a positive outcome, clearance rates for each week will be calculated as (1 – the KM survival probability estimate). The median time to clearing and 95% CI for each treatment group will also be summarized. Inverse KM curves based on (1 – the KM survival probability estimates) will be plotted to describe the estimated proportion of subjects with clearance over time for each treatment group.

## 8.2.9. Recurrence of Baseline Warts Cleared Prior to Week 12

The time to recurrence of baseline warts which have previously cleared is calculated as the number of days between the first date that baseline wart count is 0 and the first date after that for which baseline wart count is > 0. Subjects who do not have recurrence of baseline warts after clearing will be censored at the date of their last study assessment.

Kaplan-Meier estimates and plots will be presented for the time to recurrence in a similar manner to that described above for time to clearing; however as recurrence is negative outcome, the KM curves will be based on the KM survival probability estimates. Also, as clearing can occur at any visit, the KM estimates of recurrence will be based on 14 day intervals from the date of clearing: 2 Weeks (14 days), 4 Weeks (28 days), 6 Weeks (42 days), 8 Weeks (56 days), and 10 Weeks (70 days) post clearing. KM curves will be presented for each treatment arm, with Vehicle Gel subjects separated into QD and BID groups.

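### SAP 8.2.9 reads the recurrence Kaplan-Meier curve at the exact nominal visit gaps with no window allowance, so the tabulated estimates depend partly on appointment dates (minor).

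*SAP*

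**What the plan says.** SAP 8.2.9 measures time to recurrence from the first date the baseline wart count is zero to "the first date after that for which baseline wart count is > 0". On censoring it says: "Subjects who do not have recurrence of baseline warts after clearing will be censored at the date of their last study assessment". For the reading points it says that "the KM estimates of recurrence will be based on 14 day intervals from the date of clearing", tabulated at "2 Weeks (14 days), 4 Weeks (28 days), 6 Weeks (42 days), 8 Weeks (56 days), and 10 Weeks (70 days) post clearing". Under Protocol 4.2.1 recurrence is assessed at study visits, so both ends of the interval are visit dates.

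Protocol Table 4 and the SAP 11.1 schedule allow ±3 days at Week 2 (Day 14) and ±5 days at Weeks 4, 8 and 12 (Days 28, 56, 84). Every visit is dated from Baseline, not from the visit before.

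For time to clearance, SAP 8.2.8 does allow for the windows: "week will be defined by the maximum day allowable by the visit windows", with the example that "the summary for Week 2 will count all subjects with clearance on or before Day 18". SAP 8.2.9 says recurrence is handled in a similar way, but replaces this rule with exact 14-day multiples because clearing can happen at any visit.

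**The concern.** The reason given in 8.2.9 explains why time is counted from clearance. It does not explain why the window allowance is dropped. Since the reading points coincide with the nominal visit gaps, a gap one day over nominal puts a recurrence after the point that its visit was meant to inform. The tabulated recurrence estimate then reflects appointment dates as well as recurrence. Only subjects who clear are at risk, each active arm is tabulated separately, and vehicle is split into QD and BID, so few events may determine each figure.

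**Working it through.** **The SAP's own figure.** Week 2 nominal day 14, plus a 3-day window, plus 1 because in SAP 4.4.1 "the date of first dose of study medication is Day 1": 14 + 3 + 1 = 18. This reproduces the Day 18 in 8.2.8.

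**Possible gaps.** For a clearing visit with window a and a later visit with window b, the gap runs from nominal − (a + b) to nominal + (a + b).

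| Clearing to later visit | Nominal gap (days) | a + b | In-window range | A late event is counted at |
|---|---|---|---|---|
| Week 2 to 4 | 14 | 8 | 6–22 | 28 |
| Week 4 to 8 | 28 | 10 | 18–38 | 42 |
| Week 8 to 12 | 28 | 10 | 18–38 | 42 |
| Week 2 to 8 | 42 | 8 | 34–50 | 56 |
| Week 4 to 12 | 56 | 10 | 46–66 | 70 |
| Week 2 to 12 | 70 | 8 | 62–78 | none, if 71–78 |

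An early visit never brings an event forward to the preceding reading point (the shortest gaps, 18, 34, 46 and 62, exceed 14, 28, 42 and 56). The shift goes one way only.

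**Share of matching-visit recurrences that shift.** The documents give no distribution of visit dates, so this is an assumption and is varied:
- Uniform and independent, whole days: the two offsets are equal with probability 1/11, so by symmetry P(gap > nominal) = (1 − 1/11)/2 = 5/11 = 45.5% for every pair.
- Triangular within the windows: 43–44%.
- 25%, 50% or 75% of visits placed exactly on the scheduled day, the rest uniform: 42–43%, 33–34%, 19–20%.
- All visits on schedule: 0%.

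**Effect on the estimate.** Large-sample simulation (300,000 subjects), uniform timing, no dropout, assumed recurrence of 10% per 14 days, clearing equally often at Weeks 2, 4 and 8. The on-schedule value is the same Kaplan-Meier estimate with every visit on its nominal day.

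| Day | Read as in 8.2.9 | On schedule | Relative shortfall |
|---|---|---|---|
| 14 | 1.8% | 3.3% | 45% |
| 28 | 10.8% | 16.0% | 33% |
| 42 | 22.6% | 24.4% | 7% |
| 56 | 30.8% | 31.9% | 3% |
| 70 | 44.3% | 44.8% | 1% |

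With 20% per 14 days the pattern is the same: 3.7% against 6.6% at day 14, 20.5% against 30.7% at day 28, and 69.7% against 71.5% at day 70.

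**By clearing visit (10% per 14 days).**
- Week 2 clearers, day 14: 5.5% against 10%.
- Week 4 clearers, day 28: 10.4% against 19%.
- Week 8 clearers, day 28: 13.3% against 19%, about 30% low.
- Week 8 clearers, day 42: about 62% against 19%.

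The last line is an overshoot. Week 8 clearers have a single later visit, so recurrent and non-recurrent subjects leave the risk set over the same days, 18 to 38. Late events are divided by a risk set already thinned by censoring, and the product-limit estimate climbs well above the true proportion.

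**The case against.** A reader might infer that nearly half of the recurrences are left out of the analysis. The documents do not support that. The Kaplan-Meier estimate is cumulative, so a late event enters at the next reading point. Only Week 2 to Week 12 gaps of 71 to 78 days miss every tabulated point, and those remain in the plotted curves and in the by-subject listings of time to recurrence (SAP 8). The 45.5% is a consequence of assumed uniform timing, not a figure from the plan.

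A reader might also infer that recurrence is understated at every reported time. That fails too: in the equal mix the shortfall is small from day 42, and for Week 8 clearers the direction reverses.

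On consequence, the objection largely stands. SAP 8.2.9 plans no test or between-arm comparison of recurrence, the study is not powered for efficacy (SAP 4.1), the windows are the same in every arm and evaluators are blinded (SAP 4.2). No systematic bias between arms is shown. Instability from few clearers would exist whatever day the curve is read.

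What the objection does not remove is that the reading points are the nominal gaps themselves, with no allowance, in the subsection directly after one that makes the allowance.

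**Conclusion.** The point holds as a minor analysis-specification issue. As written, 8.2.9 moves an in-window recurrence with a gap of 1 to 8 days (pairs involving Week 2) or 1 to 10 days (other pairs) over nominal to the next reading point, or beyond the last. How often this happens depends on visit timing that the documents do not give: from 0% on perfect schedule to 45.5% under uniform timing. Under uniform timing, an assumed 10% recurrence per 14 days and an equal mix of clearing visits, the day-14 estimate is about half its on-schedule value, day 28 about a third low, and later points 1 to 7% low. Overlap of events and censoring at Week 12 can instead push the estimate far too high. The result affects a secondary, descriptive summary only.

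**What to change.** In SAP 8.2.9, define the event time as the nominal gap between the scheduled clearing visit and the scheduled visit at which recurrence is found, and the censoring time as the nominal gap to the last scheduled visit attended (14, 28, 42, 56 or 70 days). With in-window visits this gives the on-schedule values by construction, and it removes the Week 12 overshoot because events and censorings at one visit then share one time.

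SAP 4.4.2 labels the final visit of an early terminator as ET rather than as a week, so the sentence should assign ET visits by the SAP Table 1 windows. It should also say what happens if an ET visit falls in the same window as the clearing visit, where the nominal gap would be zero. An interval-censored estimate is an acceptable alternative.

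Do not instead read the actual-date curve at nominal plus both windows (22, 38, 50, 66, 78 days). In the same equal mix that gives 4.9%, 19.8%, 27.2%, 38.4% and 72.9%, against on-schedule values of 3.3%, 16.0%, 24.4%, 31.9% and 44.8%.

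The cost is a short SAP edit and the loss of day-level detail in the curve; actual dates stay in the listings.

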### 8.3. Tolerability Endpoints

Tolerability assessments will be performed according to the following scales:

Erythema	
Score	Description
0-None	No evidence of erythema present
1-Mild	Slight pink coloration
2-Moderate	Definite redness
3-Severe	Marked erythema, bright red to dusky dark red in color
Edema	
Score	Description
0-None	No edema
1-Mild	Mild edema; barely perceptible

2-Moderate	Moderate swelling localized to the wart and immediately adjacent skin
3-Severe	Extensive edema that involves non-treatment sites adjacent to treatment
	area

#### **Erosions/Ulceration**

Score	Description
0-None	No erosions
1-Mild	Slight erosions on some treated areas
2-Moderate	Erosions over half of the treated areas
3-Severe	Extensive full-thickness erosions over most treatment areas; or at least
	one area of ulceration

#### **Burning/Stinging**

Score	Description
0-None	No burning/stinging
1-Mild	Slight warm, burning/stinging sensation; not very bothersome
2-Moderate	Definite warm, burning/stinging sensation that is somewhat bothersome
3-Severe	Hot, tingling/sensation that has caused definite discomfort and may
	have disturbed sleep

Tolerability assessments (erythema, edema, erosions/ulcerations, burning/stinging) will be summarized using frequency distributions at baseline, Weeks 2, 4, 8, and 12/ early termination (ET), as well as the worst post-baseline assessment. The worst post-baseline assessment will be determined individually for each tolerability parameter. (e.g., the worst assessment for erythema may occur at a different visit than the worst assessment for edema.) The number and proportion of subjects with a severe assessment or a two step severity increase from baseline will be summarized by treatment group at Weeks 2, 4, 8, and 12/ET for each assessment and for any assessment. Vehicle Gel subjects will be separated into QD and BID groups. Additionally, the number and percentage of subjects who have 2 or more severe assessments at the same visit for any visit will be presented. A shift table will also be presented by tolerability parameter and treatment group, and all tolerability scores will be listed.

## 9. Safety Analysis

#### 9.1. Adverse Events

All AEs that occur during the study will be recorded and classified on the basis of Medical Dictionary for Regulatory Activities (MedDRA) terminology. Treatment-emergent AEs (TEAEs) are defined as AEs with an onset on or after the date of the first study drug dose, and occur within 30 days of the last study drug dose. Adverse events noted prior to the first study drug administration that worsen after baseline will also be reported as TEAEs and included in the summaries.

All information pertaining to an AE noted during the study will be listed by subject, detailing verbatim term given by the principal investigator or designee, preferred term, system organ class (SOC), onset date, resolution date, severity, seriousness, action taken, outcome, and drug relatedness. The event onset will also be shown relative to study drug initiation (in number of days). Listings will be provided for all TEAEs, adverse events prior to date of first treatment, and adverse events starting more than 30 days after last study drug use.

## 9.1.1. Incidence of Adverse Events

A TEAE is defined as any event not present before exposure to study drug or any event already present that worsens in either intensity or frequency after exposure to study drug. Adverse events will be deemed treatment emergent if the onset date is on or after the date of first treatment, Day 1. Events with onset date during the screening period are not treatment emergent and will be listed separately.

The total number of TEAEs and the number and percentage of subjects with at least one TEAE in each SOC and having each individual TEAE based on the PT will be presented.

## 9.1.2. Relationship of Adverse Events to Study Drug

A summary of TEAEs by relationship to study drug will be presented in a table by total number of TEAE and incidence of occurrence. The investigator will provide an assessment of the relationship of the event to the study drug as Unrelated, Unlikely, Possible, Probable, and Definite. The latter three categories would constitute "Related." If a subject reports multiple occurrences of the same TEAE, only the most closely related occurrence will be presented in the incidence count. Treatment-emergent AEs that are missing a relationship will be presented in the summary table as "Related" but will be presented in the data listing with a missing relationship. Percentages will be calculated based on the number of subjects in the safety population.

The TEAE data will be categorized and presented by SOC, PT, and relationship in a manner similar to that described in Section 9.1.1.

#### 9.1.3. Severity of Adverse Event

A summary of TEAEs by severity will be presented in a table by total number of TEAE and incidence of occurrence. The severity that will be presented represents the most extreme severity captured on the eCRF page. The possible severities are "Mild," "Moderate," and "Severe." In the TEAE severity table, if a subject reported multiple occurrences of the same TEAE, only the most severe will be presented in the incidence count. Treatment-emergent AEs that are missing severity will be presented in tables as "Severe" but will be presented in the data listing with a missing severity. Percentages will be calculated based on the number of subjects in the safety population.

The TEAE data will be categorized and presented by SOC, PT, and severity in a manner similar to that described in Section 9.1.1.

#### 9.1.4. Serious Adverse Events

Serious TEAEs will be presented in a table. At each level of subject summarization, a subject is counted once for the incidence if the subject reported one or more events. Percentages will be calculated based on the number of subjects in the safety population.

The treatment-emergent SAE data will be categorized and presented by SOC and PT in a manner similar to that described in Section 9.1.1.

# 9.1.5. Serious TEAEs, Deaths and Adverse Events Leading to Treatment or Study Discontinuation

A listing of all Serious TEAEs (including deaths) and/or AEs leading to treatment or study discontinuation will be presented. Additionally, a separate listing of any deaths will be presented. Deaths and discontinuations will be assessed based on data recorded in the AE eCRF page. Subject deaths will be identified as AEs where the outcome is "Fatal". Adverse events leading to treatment discontinuation will be identified as AEs where the action taken with study drug is "Drug Withdrawn". Adverse events leading to study discontinuation will be identified as AEs where the caused study discontinuation field is marked as "Yes".

#### 9.2. Clinical Laboratory Evaluations

The majority of laboratory assessments will be performed by a central laboratory. All summaries will be based on the units provided by the central laboratory and no conversion will be performed. Lab test names listed in the statistical analysis plan are the same as indicated in the protocol; however the tables and listings will report results using the test names based on CDISC controlled terminologies.

Blood chemistry, hematology, and PT/PTT values will be reported individually at screening, baseline, and Week 12/ET. Laboratory test results will be summarized descriptively at baseline and Week 12/ET. Changes from baseline to Week 12/ET in laboratory test results based on normal ranges will be summarized with descriptive statistics. Any clinically significant changes from baseline will be documented as an AE. Blood chemistry, hematology, and PT/PTT data will also be presented in data listings by subject.

Methemoglobin will be reported as a percentage of hemoglobin. Methemoglobin will be summarized descriptively by treatment group at baseline and Weeks 2 and 12/ET. Additionally, the change from baseline in methemoglobin will be summarized by treatment group at Weeks 2 and 12/ET. Methemoglobin data will also be presented in data listings by subject.

For the above laboratory tests, ET visits will be summarized as Week 12/ET regardless of when the visit occurs as the tests are not performed at every visit.

Urine pregnancy test results, performed at Screening, Baseline, and Weeks 4, 8, and 12, for women of child-bearing potential (WOCBP) will be presented in data listings by subject.

### 9.3. Vital Sign Measurements

Blood pressure and pulse will be summarized by treatment group from baseline through Week 12. Additionally, change from baseline in vital signs will be summarized at Weeks 2, 4, 8, and 12. Any clinically significant changes from baseline will be documented as an AE. All visit sign measurement data will be listed.

#### 9.4. Physical Examination

Any clinically significant changes from baseline will be documented as an AE. All physical examination data will be listed.

#### **10. Interim Analysis**

There will be 4 Data Safety Monitoring Board (DSMB) meetings during the conduct of this study to evaluate safety and tolerability prior to dose modification. A subset of the final safety and tolerability tables and listings, will be provided to the DSMB for review. Outputs to be provided to the DSMB are documented in the DSMB charter. No inferential statistics or hypothesis testing is planned for the DSMB analyses. DSMB analyses will be unblinded to actual treatment. The analyses for the DSMB will be performed by a separate, independent statistics team.

In addition, an Interim Analysis including efficacy summaries will be conducted upon completion of Cohorts 1 and 2 to assist in the planning of future trials. No stopping rules for futility or early efficacy assessment will be applied as part of the interim analysis. The analysis will only be conducted on the subjects in cohorts 1 and 2, and a subset of tables from the primary analysis will be presented. Pairwise comparisons will be done between each active treatment in the cohorts and Vehicle Gel and nominal p-values will be presented without adjustment. Additionally, no adjustments will be made to p-values in the final analysis as a result of the interim analysis.

The analysis set for the interim analysis will be subjects randomized into one of the first two cohorts. All subjects randomized on or prior to the last randomization date entered into IVRS for Cohort 2 will be included.

Table	Population
Table 14.1-1 Subject Disposition	All Randomized Subjects

#### Table 2: Interim Analysis Outputs

Table 14.1-2 Demographics and Baseline Characteristics	Intent-to-Treat Population		
Table 14.2-1.1 Complete Clearance of Baseline EGW/PAW at	Intent-to-Treat Population		
or Before Week 12			
Table 14.2-1.3 Complete Clearance of Baseline EGW/PAW at	Intent-to-Treat Population		
or Before Week 12 by Gender			
Table 14.2-7.1 Percent Change in Baseline EGW/PAW at	Intent-to-Treat Population		
Weeks 2, 4, 8, and 12			
Table 14.2-9.1 Count of Total Warts at Weeks 2, 4, 8, and 12	Intent-to-Treat Population		
Table 14.3-1 Study Drug Exposure (Days) and Missed Doses	Safety Population		
Table 14.3-3.1 Summary of Tolerability Evaluations	Safety Population		
Table 14.3.1-2 Treatment-Emergent Adverse Events by System	Safety Population		
Organ Class and Preferred Term	_		

## 11. Appendices

#### 11.1. Schedule of Study Procedures

PROCEDURES	Screening (Day -35 – Day -1)	Visit 1 Baseline (Day 0)	Visit 2  Week 2 ±3 days (Day 14)	Visit 3 Week 4 ±5 days (Day 28)	Visit 4 Week 8 ±5 days (Day 56)	Visit 5 Week 12/ET  ±5 days (Day 84)
Informed Consent	Х					
Demographics/Smoking	Х					
Medical History	Х	Х				
Medication History	Х	Х				
Inclusion/Exclusion	Х	Х				
Brief Physical Examination	Х	X 				Х
Chemistry, Hematology, PT/PTT	Х	X 				Х
Urine Pregnancy Test	Х	X		Х	Х	Х
Methemoglobin 	Х	X	Х			Х
Blood Pressure and Pulse	Х	Х	Х	Х	Х	Х
Wart Counts	Х	Х	Х	Х	Х	Х
Tolerability Evaluation 		Х	Х	Х	Х	Х
Instruct on Study Drug Application and Provide Subject Instructions		Х				
Dispense Dosing Diary		Х		Х	Х	
Collect Completed Dosing Diary				Х	Х	Х
Study Drug Dispensed		Х		Х	Х	
Study Drug Collected				Х	Х	Х
Subject Compliance			Х	Х	Х	Х
Concomitant Medications		Х	Х	Х	Х	Х
Adverse Events	Х	Х	Х	Х	Х	Х

 All visit dates are in reference to Baseline, e.g., Visit 2 occurs two weeks (14 days) after Baseline visit.

 All Week 12 procedures should be completed for subjects who prematurely discontinue.

 If the Baseline Visit is within 7 calendar days of the Screening visit, Physical Examination, Chemistry, Hematology, PT/PTT, and UPT do not need to be repeated.

 Collected via pulse co-oximetry at site.

 Tolerability Assessments are defined in Section 4.3 of the protocol
